Attachment 2. Protocol JNBA Clinical Laboratory Tests

Clinical Laboratory Tests

Hematology^a

Basophils
 Eosinophils
 Erythrocyte count (RBC)
 Hematocrit
 Hemoglobin
 Leukocytes (WBC)
 Lymphocytes
 Monocytes
 Neutrophils (segmented and bands)
 Platelets
 Reticulocytes

Coagulation:^a

aPTT
 PT/INR

Urinalysis^a

Blood
 Glucose
 Ketones
 pH
 Protein
 Specific gravity
 Urine leukocyte esterase

Clinical Chemistry^a
Serum Concentrations of:

Alanine aminotransferase
 Albumin
 Alkaline phosphatase
 Aspartate aminotransferase
 Blood urea nitrogen
 Calcium and ionized calcium
 Chloride
 Cholinesterase
 Creatinine
 Gamma-glutamyl transpeptidase
 Glucose, random
 LDH
 Magnesium
 Potassium
 Sodium
 Total bilirubin; if total bilirubin is increased a direct bilirubin should be obtained.
 Total protein
 Uric acid
 Tumor markers (if applicable)

Serum or Urine Pregnancy Test (females only)^a

Abbreviations: aPTT = activated partial thromboplastin time; INR = International Normalised Ratio; LDH = lactate dehydrogenase; PT = prothrombin time; RBC = red blood cells; WBC = white blood cells.

^a Local or investigator-designated laboratory

Attachment 3. Protocol JNBA Pharmacokinetic and Pharmacodynamic Sampling Schedule

Pharmacokinetic and Pharmacodynamic Sampling for Schedule 1

Cycle	Day	Collection Time	PK Sampling Time	MET ECD and EGFR ECD ^a	MET and EGFR Ligands ^a	Proteomic Blood Sample ^a
1 and 2	1	Predose	X	X	X	X
	1	Mid-infusion	X			
	1	End of infusion	X	X	X	X
	1	2 hours post end of infusion	X			
	1	4 hours post end of infusion	X			
	1	6 hours post end of infusion (Cycle 1 only)	X			
	2	24 ±4 hours post-end of infusion (Cycle 1 only)	X	X	X	X
	3	Anytime during day (Cycle 1 only)	X			
	8±1	Anytime during day	X			
	15	Predose	X	X	X	X
	15	End of infusion	X	X	X	X
	15	2 hours post end of infusion (Cycle 1 only)	X			
	15	4 hours post end of infusion (Cycle 1 only)	X			
	15	6 hours post end of infusion (Cycle 1 only)	X			
	22±2	Anytime during day (Cycle 1 only)	X			
3-6	1	Predose	X	X	X	X
	1	End of infusion	X			
Follow-ups		Occurs on the day the follow-ups occur.	X	X	X	

Abbreviations: ECD = extracellular domain; EGFR = epidermal growth factor receptor; MET = mesenchymal-epithelial transition factor; PK = pharmacokinetic; V = volume of distribution.

^a Samples are requested to be taken immediately before the dose and immediately after the end of the LY3164530 infusion. Aberrations to specified sampling times will not be considered protocol deviations as long as the samples are taken and the actual sampling time is recorded. It is essential that the actual times of LY3164530 dose and samples are recorded accurately on the appropriate forms.

Pharmacokinetic and Pharmacodynamic Sampling for Schedule 2 Cycle	Day	Collection Time	PK Sampling Time	MET ECD and EGFR ECD ^a	MET and EGFR Ligands ^a	Proteomic Blood Sample ^a
1 and 2	1	Predose	X	X	X	X
	1	Mid-infusion	X			
	1	End of infusion	X	X	X	X
	1	2 hours post end of infusion	X			
	1	4 hours post end of infusion	X			
	1	6 hours post end of infusion	X			
	2	24 ±4 hours post-end of infusion	X	X	X	X
	3	Anytime during day	X			
	8	Predose	X			
	8	End of infusion	X			
	22	Predose	X	X	X	X
	22	End of infusion	X	X	X	X
	22	2 hours post end of infusion (Cycle 1 only)	X			
	22	4 hours post end of infusion (Cycle 1 only)	X			
	22	6 hours post end of infusion (Cycle 1 only)	X			
	23	24 ±4 hours post-end of infusion (Cycle 1 only)	X			
	24	Anytime during day (Cycle 1 only)	X			
3-6	1	Predose	X	X	X	X
	1	End of infusion	X			
Follow-up		Occurs on the day the follow-ups occur.	X	X	X	

Abbreviations: ECD = extracellular domain; EGFR = epidermal growth factor receptor; MET = mesenchymal-epithelial transition factor; PK = pharmacokinetic; V = volume of distribution.

^a Samples are requested to be taken immediately before the dose and immediately after the end of the LY3164530 infusion. Aberrations to specified sampling times will not be considered protocol deviations as long as the samples are taken and the actual sampling time is recorded. It is essential that the actual times of LY3164530 dose and samples are recorded accurately on the appropriate forms.

Attachment 4. Protocol JNBA ECG, Chemistry, and Hematology Collection Schedule

Schedule 1

Cycle	Day	Collection Time	Central Triplicate ECG	Central Single ECG	Local Hematology	Local Chemistry
Screening			X		X	X
1	1	Predose	X		X	X
	1	EOI (+ 10 min)	X		X ^a	X ^a
	1	2 ±0.25 hours EOI	X			
	1	6 ±0.25 hours EOI	X			
	2	24 ±4 hours EOI	X		X ^a	X ^a
	3	48 ±4 hours EOI	X		X ^a	X ^a
	8		X		X	X
	15	Predose	X		X	X
	15	EOI (+ 10 min)	X			
	15	2 ±0.25 hours EOI	X			
2	15	6 ±0.25 hours EOI	X			
	22		X		X	X
	1	Predose		X	X	X
	8			X	X	X
	15	Predose		X	X	X
3-X	22			X	X	X
	1	Predose		X	X	X
	15	Predose		X	X	X
Follow up	28			X	X	X

Abbreviations: ECG = electrocardiogram; EOI = end of infusion; min = minute.

^a If an abnormality in hematology or chemistry is consistently observed in the 48 hours following the end of the first infusion, additional post-infusion laboratory samples (EOI, and 24 hours and 48 hours after EOI) must be repeated for subsequent infusions until they are normal or return to baseline levels.

Schedule 2

Cycle	Day	Collection Time	Central TriPLICATE ECG	Central Single ECG	Local Hematology	Local Chemistry
Screening			X		X	X
1	1	Predose	X		X	X
	1	EOI (+ 10 min)	X		X ^a	X ^a
	1	2 ±0.25 hours EOI	X			
	1	6 ±0.25 hours EOI	X			
	2	24 ±4 hours EOI	X		X ^a	X ^a
	3	48 ±4 hours EOI	X		X ^a	X ^a
	8	Predose	X		X	X
	8	EOI (+ 10 min)	X			
	8	2 ±0.25 hours EOI	X			
	8	6 ±0.25 hours EOI	X			
2-X	15	Predose		X	X	X
	22	Predose		X	X	X
	1	Predose		X	X	X
	8	Predose		X	X ^b	X ^b
	15	Predose		X	X	X
Follow up	22	Predose		X	X ^b	X ^b
	28			X	X	X

Abbreviations: ECG = electrocardiogram; EOI = end of infusion; min = minute.

- ^a If an abnormality in hematology or chemistry is consistently observed in the 48 hours following the end of the first infusion, additional post-infusion laboratory samples (EOI, and 24 hours and 48 hours after EOI) must be repeated for subsequent infusions until they are normal or return to baseline levels.
- ^b In Cycle 2-X, if clinically significant changes are observed, hematology and/or chemistry should be obtained at least weekly until no longer clinically significant. Otherwise these samples are not required.

Attachment 5. Protocol JNBA Hepatic Monitoring Tests for Treatment-Emergent Abnormality

Selected tests may be obtained in the event of a treatment-emergent hepatic abnormality and may be required in follow up with patients in consultation with the Lilly clinical research physician.

Hepatic Monitoring Tests

Hepatic Hematology^a

Hemoglobin
 Hematocrit
 RBC
 WBC
 Neutrophils, segmented and bands
 Lymphocytes
 Monocytes
 Eosinophils
 Basophils
 Platelets

Hepatic Chemistry^a

Total bilirubin
 Direct bilirubin
 Alkaline phosphatase
 ALT
 AST
 GGT
 CPK

Haptoglobin^a

Hepatic Coagulation^a

Prothrombin time
 Prothrombin time, INR

Hepatic Serologies^{a,b}

Hepatitis A antibody, total
 Hepatitis A antibody, IgM
 Hepatitis B surface antigen
 Hepatitis B surface antibody
 Hepatitis B core antibody
 Hepatitis C antibody
 Hepatitis E antibody, IgG
 Hepatitis E antibody, IgM

Anti-nuclear antibody^a

Anti-smooth muscle antibody^a

Abbreviations: ALT = alanine aminotransferase; AST = aspartate aminotransferase; CPK = creatine phosphokinase; GGT = gamma glutamyl transferase; Ig = immunoglobulin; INR = International Normalised Ratio; RBC = red blood cells; WBC = white blood cells.

^a Assayed by Lilly-designated or local laboratory.

^b Reflex/confirmation dependent on regulatory requirements and/or testing availability.

Attachment 6. Protocol JNBA Recommendations for Reporting Serious Adverse Events

Recommendations for Reporting Serious Adverse Events

When contacting Lilly to report a serious adverse event (SAE), please have the following information available:

Patient Demographics

- patient identification (number), sex, date of birth, origin, height, and weight

Study Identification

- full trial protocol number, investigator's name, investigator's number

Study Drug

- drug code or drug name, unit dose, total daily dose, frequency, route, start dose, cycle details, start date and last dose date (if applicable)

Adverse Event

- description, date of onset, severity, treatment (including hospitalization), action taken with respect to study drug, clinical significance, test and procedure results (if applicable)

Relationship to Study Drug & Protocol Procedures

Concomitant Drug Therapy

- indication, total daily dose, duration of treatment, start date, action taken

In Case of Death

- cause, autopsy finding (if available), date, relationship to study drug and protocol procedures.

Attachment 7. Protocol JNBA mTPI and Simulation

The modified toxicity probability interval (mTPI) method employs a simple beta-binomial hierarchical model. Decision rules are based on calculating the unit probability mass (UPM) of 3 intervals corresponding to underdosing, proper dosing, and overdosing in terms of toxicity. Specifically, the underdosing interval is defined as $(0, p_T - \epsilon_1)$, the overdosing interval as $(p_T + \epsilon_2, 1)$, and the proper dosing interval as $(p_T - \epsilon_1, p_T + \epsilon_2)$, where ϵ_1 and ϵ_2 are small fractions, such as 0.05, to account for the uncertainty around the true target toxicity. A sensitivity analysis reported by Ji et al. (2010) showed that the mTPI design is robust to the specification of ϵ values.

In addition, ϵ_1 and ϵ_2 could take different values to reflect physician preference and the nature of the disease. For advanced diseases with few treatment options, higher toxicity rates might be considered acceptable, implying a specification of $\epsilon_2 > \epsilon_1$. For less advanced diseases, the 2 ϵ values could be identical or ϵ_1 could be $> \epsilon_2$. The 3 dosing intervals are associated with 3 different dose-escalation decisions. The under-dosing interval corresponds to a dose escalation (E), overdosing corresponds to a dose deescalation (D), and proper dosing corresponds to staying at the current dose (S).

Given an interval and a probability distribution, the UPM of that interval is defined as the probability of the interval divided by the length of the interval. The mTPI design calculates the UPMs for the three dosing intervals, and the one with the largest UPM implies the corresponding dose-finding decision. That decision provides the dose level to be used for future patients. For example, if the underdosing interval has the largest UPM, decision E, to escalate, will be executed, and the next cohort of patients will be treated at the next-higher dose level. Ji et al. (2010) show that the decision based on the UPM is optimal in that it minimizes a subsequent expected loss. Under the mTPI design, a trial is terminated when either the lowest dose is above the maximum tolerated dose (MTD) or a pre-specified maximum sample size is reached.

Simulation

A small simulation study was conducted to compare the mTPI with 3+3 in identifying the right MTD. Six scenarios were run, each with 1000 simulated trials. As in Study JNBA, the MTD has a target toxicity probability of $P_T = 0.3$ and ϵ_1 and ϵ_2 are set at 0.013 and 0.001 respectively. The scenarios assumed the true probabilities of six doses as follows: scenario 1 = (0.1, 0.2, 0.3, 0.4, 0.5, 0.6); scenario 2 = (0.08, 0.16, 0.24, 0.3, 0.38, 0.46); scenario 3 = (0.04, 0.08, 0.12, 0.16, 0.2, 0.24); scenario 4 = (0.4, 0.5, 0.6, 0.7, 0.8, 0.9); scenario 5 = (0.04, 0.08, 0.12, 0.16, 0.2, 0.58); and scenario 6 = (0.06, 0.46, 0.53, 0.6, 0.67, 0.74). For all scenarios, the probability of selecting each dose was summarized, the average number of patients treated at each dose and average number of patients experience DLT at each dose. The simulation demonstrates that, in general, mTPI method correctly identifies the MTD more than 3+3 and appears to be as safe as 3+3 method in that it puts a similar percentage of patients on toxic doses.

Scenario	Dose Level	True Prob (tox)	Selection Prob (%)		# of Subjects Treated		# of Toxicities	
			mTPI	3+3	mTPI	3+3	mTPI	3+3
1	1	0.1	5.8	24.4	3.53	4.42	0.38	0.44
	2	0.2	20.8	30.3	6.89	4.55	1.45	0.89
	3	0.3	35.1	19.4	8.21	3.43	2.39	1
	4	0.4	28.4	4.4	6.94	1.61	2.78	0.68
	5	0.5	7.2	0.5	2.99	0.43	1.54	0.22
	6	0.6	1.3	0	1.06	0.06	0.62	0.04
2	1	0.08	3.4	20.8	2.67	4.15	0.22	0.31
	2	0.16	13.2	26.4	5.17	4.49	0.83	0.75
	3	0.24	20.6	19.5	5.81	3.69	1.38	0.91
	4	0.3	29.2	10.8	7.29	2.32	2.22	0.67
	5	0.38	23.7	2.8	5.48	1.1	2.09	0.42
	6	0.46	9.5	1.6	3.48	0.36	1.63	0.17
3	1	0.04	0.8	7.3	1.6	3.52	0.07	0.14
	2	0.08	1.7	12.1	2.07	3.88	0.15	0.33
	3	0.12	3.6	18.3	2.73	3.91	0.34	0.48
	4	0.16	8.5	16.2	3.54	3.63	0.53	0.62
	5	0.2	14.5	11.4	4.65	2.77	0.94	0.58
	6	0.24	70.8	25.4	15.38	1.74	3.62	0.41
4	1	0.4	43.3	15.6	13.7	4.94	5.4	1.97
	2	0.5	10.5	1.5	5.25	1.34	2.63	0.69
	3	0.6	1.2	0	1.67	0.19	1	0.11
	4	0.7	0	0.1	0.44	0.01	0.3	0
	5	0.8	0	0	0.1	0.01	0.07	0.01
	6	0.9	0	0	0.02	0	0.02	0
5	1	0.04	0.8	5.9	1.48	3.49	0.05	0.14
	2	0.08	2.1	13.2	2.22	3.89	0.17	0.31
	3	0.12	4	16.8	2.85	3.95	0.35	0.51
	4	0.16	9.8	18.7	3.86	3.68	0.64	0.61
	5	0.2	75.7	24.6	14.12	3.37	2.86	0.67
	6	0.58	7.3	3.7	5.38	1.61	3.17	0.94
6	1	0.06	60.4	76.8	14.01	5.62	0.81	0.33
	2	0.46	31.2	8.5	10.5	4.43	4.83	2.07
	3	0.53	7.1	0.8	3.64	0.87	1.91	0.47
	4	0.6	0.8	0	1.21	0.09	0.73	0.05
	5	0.67	0	0.1	0.39	0.01	0.27	0
	6	0.74	0	0.1	0.11	0.01	0.08	0

Abbreviation: mTPI = modified toxicity probability interval.

**Attachment 8. Protocol JNBA Protocol I7-MC-JNBA(b)
Amendment Summary A Phase 1 Study of LY3164530, a
Bispecific Antibody Targeting MET and EGFR, in Patients
with Advanced or Metastatic Cancer**

Overview

Protocol I7-MC-JNBA, A Phase 1 Study of LY3164530, a Bispecific Antibody Targeting MET and EGFR, in Patients with Advanced or Metastatic Cancer has been amended. The new protocol is indicated by Amendment (b) and will be used to conduct the study in place of any preceding version of the protocol.

- Introduction of a new weekly schedule for dosing.
- Minor changes were made to increase the clarity and consistency of the document and to correct typographical errors.

Revised Protocol Sections

Note: All deletions have been identified by ~~strikethroughs~~.
All additions have been identified by the use of underscores.

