6.2. Summary of Study Design

Study JNBA is a multicenter, nonrandomized, open label, dose escalation Phase 1 study of IV LY3164530 in patients with advanced and/or metastatic cancer. Eligible patients will receive LY3164530 as an infusion on Days 1 and 15 (Schedule 1) or on Days 1, 8, 15, and 22 (Schedule 2) of each cycle. A cycle will consist of 28 days and the schedules will enroll in parallel.

Dose escalation will be driven by a modified toxicity probability interval (mTPI) method. The RP2D and schedule will be determined once at least 10 patients, but no more than 20, are treated at a dose and schedule that is at or below the maximum tolerated dose (MTD). The actual sample size for Study JNBA is anticipated to be approximately 50 patients depending on the incidence of DLTs.

The planned duration of treatment is 2 cycles. Patients who are receiving benefit from study drug may continue to be treated with LY3164530 until 1 or more of the criteria for discontinuation have been fulfilled (Section 6.3.1).

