7.2.2.3. Dose Escalation Method

Dose escalation will be driven by a mTPI method (Ji and Wang 2013) (Attachment 7). A 3+3 design is commonly used in Phase 1 trials due to its simple, intuitive, and pre-specified escalation rules. However, the 3+3 method has been criticized for being conservative because the method is dictated by the observed DLT rate without acknowledging the variability arising from small cohort size.

Like the 3+3 design, the mTPI method incorporates pre-specified escalation rules. In contrast, the mTPI method is based on quantitative models that incorporate uncertainty into the decision

rules, thereby allowing more aggressive dose escalation. In the mTPI method, the number of patients in each cohort is not fixed, but a minimum of 3 patients are required for this study at each dose (unless the rule in the table indicates to deescalate the dose due to unacceptable toxicity [DU]). If 3 to 6 patients are enrolled in a cohort, the escalation rule parallels a traditional 3+3 design. However, the stay/deescalation rule of the mTPI is more aggressive than the 3+3 design. For instance, with 2 to 3 DLTs per 6 patients enrolled, the mTPI would recommend staying at the current dose, whereas the 3+3 design would recommend deescalation. [Figure JNBA.1](#) provides the mTPI escalation rules for any cohort size up to 20 patients.

In [Figure JNBA.1](#), the number of patients dosed at a given dose level are shown in the columns (x-axis), while the number of DLTs experienced are shown in the rows (y-axis). The rules in this figure will be used for each dose level evaluated; the patient numbers and DLTs do not carry over from cohort to cohort. By locating the intersection of the number of patients dosed and the number of DLTs, 1 of 4 pre-defined rules is used:

- E: Escalate the dose
- S: Stay at the same dose
- D: Deescalate the dose
- DU: Deescalate the dose due to unacceptable toxicity. The dose cannot be re-escalated to this dose level at a future point in the escalation.

If agreed upon by the investigators and Sponsor (for instance, if PK/PD data suggest that increasing the dose further is not expected to yield additional benefit), a more conservative rule may be applied. For instance, if the rule indicates “E” to escalate, the dose may remain at the current dose level or be deescalated to a lower level.

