As shown in [Figure JNBA.1](#), if 1 of 3 patients experiences a DLT, the decision (located in column 3 row 1) is “S”, stay at the same dose. Therefore, the next patient must be treated at the same dose level. If 1 of 6 patients experience a DLT, the decision (located at column 6 row 1) is “E”, escalate the dose. However, if 2 of 3 patients experience a DLT the decision is “D” and the dose must be deescalated.

In the mTPI, the cohort size is not fixed. However, each cohort in this study will contain a minimum of 3 patients, unless the escalation rules dictate that the dose should be deescalated due to unacceptable toxicity (“DU”). Doses can be escalated, deescalated, and re-escalated following the rules in [Figure JNBA.1](#). If the dose decision was “DU,” the dose cannot be re-escalated to that level.

This study is designed to identify a dose level with a dose-limiting target toxicity rate of 30%. In reality, the exact target toxicity rate is almost never achieved for a dose. To this end, instead of using a single target rate, the mTPI method considers an equivalence interval (EI) around the target toxicity rate. For this study, the EI is calibrated to be (28.7%, 30.1%), resulting in the rules in [Figure JNBA.1](#). If the observed toxicity rate exceeds 40% and the model is still recommending “S”, the Sponsor, in discussion with the investigators, may choose to deescalate. Deescalation may not be required for toxicities confounded by patient comorbidities or other clinical factors that make direct attribution to study drug difficult to determine, particularly if

they are deemed non-serious (eg, fatigue, anorexia), reversible, or inconsistent with the known toxicities of MET or EGFR inhibitors by study investigators and the Lilly CRP/CRS.

		Number of patients treated at current dose																			
		1	2	3	4	5	6	7	8	9	10	11	12	13	14	15	16	17	18	19	20
Number of DLTs	0	E	E	E	E	E	E	E	E	E	E	E	E	E	E	E	E	E	E	E	E
	1	D	S	S	S	S	E	E	E	E	E	E	E	E	E	E	E	E	E	E	E
	2		DU	D	S	S	S	S	S	S	S	E	E	E	E	E	E	E	E	E	E
	3			DU	DU	D	S	S	S	S	S	S	S	S	S	S	E	E	E	E	E
	4				DU	DU	DU	D	D	S	S	S	S	S	S	S	S	S	S	S	S
	5					DU	DU	DU	DU	DU	D	S	S	S	S	S	S	S	S	S	S
	6						DU	DU	DU	DU	DU	DU	D	S	S	S	S	S	S	S	S
	7							DU	D	D	S	S	S	S	S						
	8								DU	D	S	S									
	9									DU	D										
	10										DU										
	11											DU									
	12												DU								
	13													DU							
	14														DU						
	15															DU	DU	DU	DU	DU	DU
	16																DU	DU	DU	DU	DU

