10.1. General Considerations

Statistical analysis of this study will be the responsibility of Lilly.

The interpretation of the study results will be the responsibility of the investigator with the Lilly CRP/CRS, pharmacokineticist, and statistician. The CRP/CRS and statistician will also be responsible for the appropriate conduct of an internal review for both the final study report and any study-related material to be authorized by Lilly for publication.

The analyses for this study will be descriptive, except for possible exploratory analyses as deemed appropriate. Data analyses will be provided by dose levels and for all patients combined wherever appropriate. For continuous variables, summary statistics will include number of patients (N), mean, median, standard deviation, standard error (SE), minimum, and maximum. Categorical endpoints will be summarized using N, frequency, percentages, and associated SE. Missing data will not be imputed. Exploratory analyses of the data that are not described in the protocol will be conducted as deemed appropriate.

This is a Phase 1 study with an open-label, dose escalation design. Patients will be enrolled into cohorts sequentially without randomization to dose level. During dose escalation, the total sample size per cohort will be guided by the mTPI method and determined by the occurrences of DLTs (up to 20 patients per cohort before establishing the RP2D and schedule). The total sample size is anticipated to be approximately 50 patients.

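### The mTPI results in Protocol Attachment 7 cannot come from the trial's three-patient-minimum rule, contradict the safety sentence printed above them, and differ from the SAP table that states the same inputs

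*Protocol*

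**What the plan says.** Protocol Section 7.2.2.3 sets the enrolment rule: "a minimum of 3 patients are required for this study at each dose", with an exception only for a DU decision. It repeats that "each cohort in this study will contain a minimum of 3 patients", with the same exception. SAP Section 6.13 carries the same rule. Section 7.2.2.3 also tells the reader that "the stay/deescalation rule of the mTPI is more aggressive than the 3+3 design".

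Attachment 7 compares mTPI with 3+3 using the trial's target (0.30) and epsilons (0.013 and 0.001), six scenarios of six doses, and 1000 trials per scenario. Its safety conclusion is that mTPI "appears to be as safe as 3+3 method in that it puts a similar percentage of patients on toxic doses". It does not define a toxic dose. It gives no cohort size, prior, start dose or DU cutoff, and does not say whether the three-patient minimum was applied. On trial size it says only that a trial can end when "a pre-specified maximum sample size is reached".

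SAP Appendix 1 gives the same target, epsilons, scenarios, replicate count and concluding sentence, above a different results table.

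**The concern.** The sentence in Attachment 7 is the plan's comparative reassurance on safety for a method that the protocol itself calls more aggressive than 3+3. An ethics board or investigator relying on it would take the extra exposure to toxic doses to be negligible. The table below it shows 2.2 to 3.3 times the 3+3 share in three of the four scenarios where the shares can differ. Separately, mean enrolments below 3 at the lowest dose suggest that the simulated design is not the trial's design. With two tables for one stated set of inputs, a reader cannot tell which operating characteristics apply.

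**Working it through.** **Inputs.** Target, epsilons, true DLT probabilities and printed columns come from Attachment 7 and SAP Appendix 1. The three-patient rule and the grid come from Protocol 7.2.2.3 and Figure JNBA.1.

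**1. Can the mTPI column come from the three-patient rule?** Below 3 patients, the only DU cell in Figure JNBA.1 is 2 DLTs in 2 patients. A trial starting at dose 1 therefore treats 2 patients there with probability p² and at least 3 otherwise:

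mean at dose 1 ≥ 2p² + 3(1 − p²) = 3 − p²

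| Scenario | p at dose 1 | Floor | Protocol | SAP |
|---|---|---|---|---|
| 2 | 0.08 | 2.994 | 2.67 | 4.500 |
| 3 | 0.04 | 2.998 | 1.60 | 3.561 |
| 5 | 0.04 | 2.998 | 1.48 | 3.648 |

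No simulated trial could have fewer than 2 patients at dose 1, so 1.60 and 1.48 are not sampling error. At dose 2 in scenarios 3 and 5, 0 DLTs in 3 at dose 1 leads to E, so the floor is 0.96³ × (3 − 0.08²) = 0.885 × 2.9936 = 2.65. The protocol prints 2.07 and 2.22.

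The start dose is unstated, but no other start dose helps. Doses 2 and 3 also average below 3 in scenarios 3 and 5 (2.07 and 2.73; 2.22 and 2.85). In scenario 4, doses 4 to 6 average 0.44 or less.

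**2. Shares on toxic doses, from the printed columns.** Share = patients on doses with true probability above 0.30 ÷ all patients.

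| Scenario | Protocol mTPI | Protocol 3+3 | SAP mTPI | SAP 3+3 |
|---|---|---|---|---|
| 1 | 10.99/29.62 = 37.1% | 2.10/14.50 = 14.5% | 5.037/29.946 = 16.8% | 1.800/14.040 = 12.8% |
| 2 | 8.96/29.90 = 30.0% | 1.46/16.11 = 9.1% | 2.985/30.000 = 10.0% | 1.380/15.879 = 8.7% |
| 5 | 5.38/29.91 = 18.0% | 1.61/19.99 = 8.1% | 3.357/30.000 = 11.2% | 1.788/20.304 = 8.8% |
| 6 | 15.85/29.86 = 53.1% | 5.41/11.03 = 49.0% | not used | not used |

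No dose in scenario 3 and every dose in scenario 4 exceeds 0.30, so those shares are equal by construction. SAP scenario 6 is only partly visible in the text available. With a cut at 0.40, the protocol shares are 13.7% vs 3.4%, 11.6% vs 2.2% and 18.0% vs 8.1% in scenarios 1, 2 and 5.

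**3. Protocol against SAP.** The mTPI selection of dose 6 in scenario 3 is 70.8% in the protocol and 46.7% in the SAP. With 1000 trials each, z = 0.241 / √(0.708×0.292/1000 + 0.467×0.533/1000) = 11.3. For dose 5 in scenario 5 (75.7% vs 55.8%), z = 9.6.

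The 3+3 selection columns disagree too. Trials selecting no dose (100% minus the column sum) in scenarios 1, 2, 3 and 5 are 21.0%, 18.1%, 9.3% and 17.1% in the protocol, and 9.4%, 6.9%, 29.5% and 5.8% in the SAP.

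**4. Likely source (inference).** I simulated mTPI from dose 1 to N = 30, with a Beta(1,1) prior, interval 0.287 to 0.301, and DU if P(p > 0.30) > 0.95. These assumptions reproduce rows 0 to 6 of Figure JNBA.1. N = 30 is taken from the printed mTPI totals (29.6 to 30.0 except in scenario 4).

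- One-patient cohorts reproduce the protocol's patient column: 36 of 36 cells within 3 Monte Carlo standard errors. Cohorts of 3 match 3 of 36. Single entry with a minimum of 3 matches 2 of 36.
- Cohorts of 3 reproduce the SAP column: 33 of 34 visible cells, the other at 3.1 standard errors. Every visible SAP mTPI mean × 1000 is a multiple of 3.

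**5. What the trial's rule might give.** Shares above 0.30 with single entry and a minimum of 3; the 3+3 range covers variants with and without expansion to 6 at the MTD.

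| Scenario | N = 30 | N = 50 | N = 50, stop at 20 on a dose | 3+3 |
|---|---|---|---|---|
| 1 | 15.7% | 18.5% | 20.5% | 14.3–15.2% |
| 2 | 9.8% | 13.8% | 15.4% | 9.1–9.5% |
| 5 | 9.9% | 10.4% | 11.7% | 9.2–9.8% |
| 6 | 44.8% | 35.5% | 46.5% | 50.0–59.3% |

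N = 50 and the stop at 20 are a sensitivity range suggested by Protocol 6.2 ("The actual sample size for Study JNBA is anticipated to be approximately 50 patients") and 10.1 ("up to 20 patients per cohort before establishing the RP2D and schedule"). They are not the documents' simulated settings.

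**The case against.** The strongest reply is that Attachment 7 never claims to have applied the three-patient minimum. It is a small generic comparison on a six-dose ladder, and the link it draws to the trial covers only the target and epsilons. No mTPI cell is shown to be miscalculated, since one-patient cohorts reproduce the column. This is fair as to wording. But a comparison offered to support the trial's method should describe the method in use, and the conflict between sentence and table stands whatever cohort size was simulated.

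Second, the SAP is out of step generally. Version 1 was approved before first dosing, describes one schedule, and sets data reviews at 5 and 10 patients against 6 and 15 in the amended protocol. Unstated cohort sizes could explain two different tables. That may be how the mismatch arose, but readers still have two results under one description. The first two parts of the finding need only the protocol.

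Third, with the minimum applied at N = 30, the shares are close to 3+3 and the sentence might largely survive. That is possible. The gap in scenarios 1 and 2 widens at N = 50, so the outcome depends on settings that are not disclosed.

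Three narrower points are accepted:

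- The 40% in Section 7.2.2.3 ("If the observed toxicity rate exceeds 40% and the model is still recommending") is an observed rate, so the 0.40 cut here is only a sensitivity check.
- Neither document, in the text available, says how a trial that clears the top dose is counted. Part of the SAP appendix is not visible, so nothing firmer can be said of it.
- The SAP 3+3 no-selection rates are close to a rerun that counts a cleared top dose as no selection (9.5–10.5%, 7.7–8.3%, 26.5–29.9%, 4.2–6.1%). The protocol column fits neither that convention nor the alternative (9.3–10.4%, 6.5–6.8%, 1.8%, 1.6–1.8%).

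**Conclusion.** The concern holds and should be fixed. The contradiction between sentence and table is read directly from printed figures and survives either cut. The breach of the three-patient floor is exact arithmetic and does not depend on which single dose the trials started from. The disagreement with the SAP is far beyond the error of 1000 trials.

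That cohort size is the cause (1 in the protocol, 3 in the SAP) is an inference from fit, resting on the assumed prior, DU cutoff and N. The corrected shares cannot be stated in advance because they depend on maximum N and any per-dose cap. Figure JNBA.1 and the decisions taken from it are unaffected.

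**What to change.** Rerun the simulation once under the trial's stated rule: at least 3 patients per dose unless DU, then the Figure JNBA.1 decisions. State the start dose, later cohort size, maximum N, any per-dose cap, prior, DU cutoff, MTD selection rule, 3+3 variant, and how a trial that clears the top dose is counted. Recheck both 3+3 selection columns in the process.

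Print the same table in Attachment 7 and SAP Appendix 1. Define a toxic dose, report the percentage of patients on doses above 30% for each scenario, and write the safety sentence from those figures after the rerun. The percentage of trials selecting such a dose can be summed from the same table and may be added.

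The cost is one small rerun, one table in two documents and one sentence. The comparison with 3+3 may come out less favourable than the present wording.
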